5.2 ASSESSMENT OF SAFETY

Safety will be assessed descriptively based on:

- Adverse events (including drug-related AEs and AEs leading to discontinuation)
- Adverse events of special interest (AESI)
- Serious adverse events (SAEs)
- Safety laboratory tests
- Physical examination
- Vital signs (blood pressure, pulse rate, body temperature)
- 12-lead ECG
- Immunogenicity (ADA)

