6.2.3 End of Treatment and Trial Completion

For all treated patients termination of trial medication and trial completion must be recorded on the corresponding eCRF.

For the comprehensive list of the trial procedures required at the EOT and the EOS visits please refer to [Flow Chart](#).

The EOS visit must be performed 16 weeks after the date of last drug administration.

Early Treatment and Trial Discontinuation:

If trial treatment is discontinued prematurely prior to the planned [Flow Chart](#) EOT visit, every effort should be made to have the patient return and undergo the procedures for the EOT visit as well as the EOS visit 16 weeks after the last study drug administration as outlined in the [Flow Chart](#).

Patients who are unable to physically return to the study site for the EOT and EOS visits should be contacted by the site by phone to collect information pertaining to adverse events and changes to concomitant therapy.

Trial Completion:

Trial completion is defined as a patient having reached the EOS visit within the specified window per protocol.

Treatment Completion:

Treatment completion is defined as a patient completing Visit 52 which is the EOT visit after receiving approximately 4 years of treatment

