6. GENERAL ANALYSIS DEFINITIONS

6.1 TREATMENT(S)

For basic study information on the treatment to be administered, assignment to treatment, and selection of dose, cf. Section 4 of the CTP.

All patients will receive subcutaneous doses of 600 mg of BI 655130 solution for SC injection (every four weeks).

The following trial phases are defined:

Table 6.1: 1 Flow chart of trial phases

Trial phase	Description	Start (included)	End (excluded)
Open label Treatment phase	On-treatment period	Date of start of injection of first study drug (Day 1)	EoT visit date + 1 day
Follow-up phase	Off-treatment follow-up period	EoT visit date + 1 day	Date of EoS Participation visit + 1 day

Dates are defined individually per patient. If more than one date is associated with a specific visit, measurements associated with a specific date are assigned to a study analysis phase according to the rules specified in the table. An analysis phase will not extend beyond the start date of the following phase.

EoT = End of treatment; EoS = End of study;

Patients who discontinue the treatment but will continue on trial visits will be included in analyses with the available data. For patients who discontinue the trial prematurely only available data will be used in the analyses.

The time windows for data presentation in the analysis are described in [Table 6.7: 1](#).

Treatment group will be labelled as follows: "**Speso 600 mg SC q4w**" (i.e., patients receiving BI 655130 600 mg). In addition, the descriptive statistics will be presented for the following groups:

- By treatment received in the parent trial (1368-0032):
 - "Placebo" followed by "Speso 600 mg SC q4w"** – patients who were randomised to receive placebo in the double-blind period of the parent trial and received Speso treatment in the open-label period of the parent trial
 - "Placebo" followed by "no Speso 600 mg SC q4w"** – patients who were randomised to receive placebo in the double-blind period of the parent trial and

didn't receive Speso treatment in the open-label period of the parent trial (but didn't discontinue the parent study prematurely)

- **"Speso 600 mg SC q4w" followed by "Speso 600 mg SC q4w"** – patients who were randomised to receive active treatment (Speso) in the double-blind period of the parent trial and received Speso treatment in the open-label period of the parent trial

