Disposition of the patient population participating in the trial (overall) will be summarised by presentation of the frequency of patients entered, treated, entered but not treated, who completed all doses of trial medication as planned (until the trial termination), who prematurely discontinued study drug administration by reason, who completed the observational period as planned, who prematurely discontinued study participation. Disposition will be listed by country.

The frequency of patients with iPDs will be presented for the SAF, overall. The iPDs will be listed per patient indicating whether or not the iPD led to exclusion from patient sets analysed.

The frequency of patients in each of the different analysis sets will also be overall.

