7.8.1 Adverse Events

AEs will be coded with the most recent version of MedDRA.

The analyses of AEs will be descriptive in nature. All analyses of AEs will be based on the number of patients with AEs and not on the number of AEs. System organ classes (if applicable) will be sorted according to the standard sort order specified by the EMA, preferred terms (if applicable) will be sorted by total frequency (within system organ class) across all treatment arms.

For further details on summarization of AE data, please refer to “Analysis and Presentation of Adverse Event Data from Clinical Trials” [BI-KMED-BDS-HTG-0066] (4) and “Handling of missing and incomplete AE dates” [BI-KMED-BDS-HTG-0035] (3).

The analysis of AEs will be based on the concept of treatment emergent AEs. If only the start date of an AE is collected (without start time), any AE occurrence on the same day as the first BI 655130 administration will be assigned to the on-treatment phase.

An overall summary of AEs will be presented by treatment.

This overall summary will include summary statistics for the class of other significant AEs (sponsor definition based on ICH E3 (6)) and for the class of AESIs.

The following are considered an AESI in this trial:

- Hepatic injury
- Systemic hypersensitivity reactions including anaphylactic reaction
- Severe infections (according to RCTC grading in the ISF)
- Opportunistic and mycobacterium tuberculosis infections

The investigator has to classify on the eCRF whether an observed AE was an AESI or not. Only those AEs that are indicated by the investigator as AESI in the eCRF will be analysed in this category.

Based on the specification provided in ICH E3 (6), the sponsor has defined AEs which are to be classified as ‘other significant’. These will include those non-serious AEs which were reported with ‘action taken = Drug withdrawn’ or ‘action taken = Dose reduced’.

The frequency of patients with AEs will be summarised by treatment, primary system organ class and preferred term. AEs which were considered by the investigator to be drug related will be summarised separately (secondary safety endpoint of this trial). Separate tables will also be provided for patients with SAEs, patients with drug-related SAEs, patients with AESIs, patients with AE leading to discontinuation of the trial, and patients with other significant AEs (as described previously). AEs will also be summarized by maximum RCTC grade.

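### The SAP's AE discontinuation table is keyed to leaving the trial, so a serious AE that stops trial drug in a patient who stays on falls outside both AE tables concerned with stopping

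*SAP*

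**What the plan says.** Protocol 5.2 lists among the safety assessments "Adverse events (including drug-related AEs and AEs leading to discontinuation". It does not say whether discontinuation means of drug or of the trial.

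SAP 7.8.1 turns this into a table of "patients with AE leading to discontinuation of the trial". The same section defines a class of 'other significant' AEs: "These will include those non-serious AEs which were reported with" an action taken of drug withdrawn or dose reduced. It also announces the serious-event tables: "Separate tables will also be provided for patients with SAEs, patients with drug-related SAEs". No breakdown of those tables by action taken is described.

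The SAP elsewhere distinguishes stopping drug from leaving the trial. SAP 6.1 says "Patients who discontinue the treatment but will continue on trial visits will be included in analyses with the available data", and then, as a different case, "For patients who discontinue the trial prematurely only available data will be used in the analyses". The disposition summary in SAP 7 likewise counts patients "who prematurely discontinued study drug administration by reason" separately from those who end study participation early.

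The protocol draws the same line in 3.3.4. For a patient who stops drug early, 6.2.3 says "every effort should be made to have the patient return and undergo the procedures for the EOT visit as well as the EOS visit", the latter 16 weeks after the last dose.

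**The concern.** The trial's purpose is long-term safety, and which events make patients stop the drug is a natural question to ask of it. A reader of the report would look for the answer in the discontinuation table. As named, that table answers a different question, namely which events made patients leave the trial. A patient taken off drug because of an AE is expected to stay under observation, so the two sets of patients need not overlap much. The 'other significant' class picks up the non-serious drug-stopping events but excludes the serious ones by definition.

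At stake is the reading of a low count. With about 40 patients planned (at most 45, Protocol 7.5), one patient is 1/40 = 2.5%, or 1/45 = 2.2%. One or two patients missing from the table would therefore visibly change the apparent tolerability of the drug.

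**Working it through.** The plan gives no figure to reproduce. The check classifies every AE that stops trial drug by seriousness and by whether the patient stays in the trial, and applies the SAP 7.8.1 definitions to each class.

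| AE that stops trial drug | Trial-discontinuation table | 'Other significant' AEs | SAE table |
|---|---|---|---|
| a: non-serious, patient stays | no | yes | no |
| b: non-serious, patient leaves because of it | yes | yes | no |
| c: serious, patient stays | **no** | **no** | yes |
| d: serious, patient leaves because of it | yes | no | yes |

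All four classes are also in the general AE tables by system organ class and preferred term. Let the letters stand for numbers of patients, with one drug-stopping AE each:

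- Patients with an AE that stopped drug: a + b + c + d.
- In the trial-discontinuation table: b + d, so it falls short by a + c.
- In the 'other significant' class: a + b. Its dose-reduced limb should add nothing, because Protocol 4.1.4 does not permit dose changes.
- In at least one of the two: a + b + d. Class c is in neither.

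Class c follows the course that the protocol expects. Protocol 5.2.5 has every malignancy detected in the trial reported as an SAE. Protocol 4.2.1 has trial medication, not participation, stopped for a malignancy, with listed exceptions. Such a patient who attends the end-of-study visit is a class c case.

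Illustration only, since the documents give no rates. Assume that 4 of 40 patients (10%) stop drug because of an AE and that 1 to 2 of these events are serious.

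- If all four patients stay in the trial, the trial-discontinuation table shows 0. The 'other significant' class shows 4 − 1 = 3 or 4 − 2 = 2, and 1 to 2 patients are in neither.
- If all four leave because of the event, the trial-discontinuation table shows 4, and nobody is missed.

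Under this assumption the table can therefore show anything from 0 to 4, depending only on whether patients stay for follow-up.

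**The case against.** The strongest reply is that nothing is hidden. Serious events are tabulated by patient, with further tables for drug-related SAEs and for AEs of special interest. The user-defined concepts add serious infections, malignancies and hypersensitivity. SAP 7 promises listings of all individual values. Disposition counts early drug discontinuation by reason, SAP 6.6.1 reports reasons for withdrawal from treatment as recorded on the eCRF, and Protocol 3.3.4.1 names adverse events among the medical reasons for stopping. This stands. A reader might infer that drug-stopping serious events vanish from the report, or that no table would give the number of patients who stopped for an AE. The documents support neither inference. What these displays do not give, as described, is the terms and seriousness of the stopping events together in one table: the SAE tables carry no action-taken split, and disposition carries no AE terms.

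A reader might also infer that the discontinuation table will be all but empty. That does not follow. Protocol 6.2.3 asks only for every effort and provides for patients who cannot return, and an event that also ends participation is counted.

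Nor does the SAP contradict the protocol, since Protocol 5.2 leaves open what is discontinued.

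Finally, the wording may be a slip for trial drug. SAP 7.8.1 refers to a sponsor standard for AE presentation that is not available here, and the list that should follow the opening words of SAP 5.4.1 is absent from the public text. Either may already call for the right table. This lowers the certainty that a table is missing. It does not remove the need to correct the phrase, because SAP 6.1 uses leaving the trial as a distinct state and a programmer would be entitled to take SAP 7.8.1 at its word.

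**Conclusion.** The point holds as a reporting defect. Followed literally, the named table undercounts AEs that led to stopping trial drug, and serious ones in patients who stay in the trial are in neither of the two AE tables concerned with stopping. No AE table named in the visible SAP text shows by term all such events, serious and non-serious.

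The size cannot be derived. It equals the number of patients who stop drug for an AE and remain in the trial (a + c above), of whom the serious cases (c) are also outside the 'other significant' class. The conclusion rests on the literal wording and on patients following the protocol's path to the end-of-study visit. It would fall away if the unseen sponsor standard or the SAP 5.4.1 list already specifies a table keyed to drug withdrawal.

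The primary endpoint and the efficacy summaries are unaffected. The trial is descriptive throughout, so no test, sample size or error rate is involved. The change should be made, but the defect does not threaten the trial.

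**What to change.** In SAP 7.8.1, replace the phrase with: *patients with AEs leading to discontinuation of trial drug (action taken = drug withdrawn), serious and non-serious*. Present it by system organ class and preferred term, like the other AE tables. Keep AEs leading to discontinuation of the trial as a separate, clearly labelled line if wanted; the two can differ in both directions, since a patient already off drug may leave during follow-up because of a new event.

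If the sponsor's AE standard already produces this table, a sentence in SAP 7.8.1 saying so is enough.

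The cost is one phrase and one table. The action-taken item is already used to define 'other significant' AEs, so no new data are needed. Some patients will appear both here and in the SAE or 'other significant' tables, which is harmless because these displays answer different questions.

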7.8.2 Laboratory data

The analyses of laboratory data will be descriptive in nature and will be based on BI standards (5). Note that data from the central Laboratory will be used for all displays described below, unless otherwise specified.

For continuous safety laboratory parameters, normalized values will be derived. Normalisation means transformation to a standard unit and to a standard reference range. The process of normalisation, handling of repeat values at the same visit for by-visit displays, as well as standard analyses for safety laboratory data are described in the BI guidance for the “Handling, Display and Analysis of Laboratory Data” (5). All analyses considering multiple times of the ULN (as described below) will be based on standardized and not normalized values. For continuous safety laboratory parameters, differences to baseline will be calculated.

Only patients with at least one available post-baseline value will be included in the analysis of an individual laboratory parameter. All individual laboratory data will be listed. Values outside the reference range will be flagged.

Descriptive statistics of laboratory values over time and for the difference from baseline (see Section 6.7) will be based upon normalised values and provided by visit, including summaries of the last value on treatment, the minimum value on treatment and maximum value on treatment.

Laboratory values will be compared to their reference ranges; shift tables will be provided for the number of patients with a specific RCTC grade at baseline versus the grade at the last measurement on treatment, as well as the worst grade on treatment. These analyses will be based on standardized laboratory values.

Potentially clinically significant abnormalities will be identified based on BI standard rules which are based on normalized converted lab values, i.e. using SI units. These rules will be listed in the SDL appendix of the CTR. Frequency tables will summarize the number of patients with potentially clinically significant abnormalities. Patients having an abnormal lab value at baseline will be presented separately. A separate listing will present potentially clinically significant abnormal lab values.

The frequency of patients with AST or ALT elevations $\geq 3xULN$, $\geq 5xULN$, $\geq 10xULN$, and $\geq 20xULN$ will be displayed based on standardized laboratory values. To support analyses of liver related adverse drug effects, the frequency of patients with AST and/or ALT $\geq 3xULN$ combined with a total bilirubin $\geq 2xULN$ in a 30 day period after AST/ALT elevation will be displayed, stratified by alkaline phosphatase $< 2xULN$ and $\geq 2xULN$ (a patient can potentially be in both alkaline phosphatase strata in case of multiple AST/ALT and bilirubin elevations). The start of the 30 day time span is triggered by each liver enzyme elevation above the defined thresholds. This analysis will be based on standardized laboratory values. A graphical analysis of the ALT and total bilirubin during the on-treatment period will also be performed; the so called eDISH plot. In the graph, for each subject, the peak total bilirubin is presented as a fold increase over the ULN against the peak ALT as a fold increase over the ULN, on a log₁₀ scale. The measurements displayed of total bilirubin and ALT may, or may not, occur on the same date. Two reference lines, 2xULN for total bilirubin and 3xULN for ALT, are drawn onto the graph in order to divide the plane into four quadrants. Normal cases are in the lower left quadrant, potential DILI cases are in the upper right quadrant (Hy's Law quadrant), while the lower right quadrant is known as the Temple's corollary range (ALT $\geq 3xULN$ and total bilirubin $< 2xULN$).

Clinically relevant findings in laboratory data will be reported as baseline conditions (at screening) or as AEs (during the trial) if judged clinically relevant by the investigator, and will be analysed as such.

7.8.3 Vital signs

The analyses of vital signs (blood pressure, pulse rate, body temperature and body weight) will be descriptive in nature.

Descriptive statistics of vital signs over time and for the difference from baseline (see [Section 6.7](#)) will be provided by treatment, including summaries of the last value during the on-treatment period, the minimum value during on-treatment period, and the maximum value during on-treatment period (see [Table 6.1: 1](#) for definition of the on-treatment period).

Clinically relevant findings in vital signs data will be reported as baseline conditions (at screening) or as AEs (during the trial) if judged clinically relevant by the investigator, and will be analysed as such.

7.8.4 ECG

Abnormal findings in 12-lead ECG will be reported as baseline conditions (at screening) or as AEs (during the trial) if judged clinically relevant by the investigator, and will be analysed as such.

No separate listing or analysis of ECG data will be prepared.

7.8.5 Others

Injection reactions including anaphylactic reaction

Injection reactions will be summarized overall, with the frequency and percentage of patients who experienced any injection reaction, both overall and specifying anaphylactic reaction as part of the table presenting patients with adverse events of special interest (AESI).

Immunogenicity

The frequency and percentage of patients with ADAs to BI 655130 will be presented by treatment, by visit and overall, if sufficient data is available.

Further exploratory assessments of the ADA data (e.g., relationship between ADA and PK) might be performed once data is available and these will be described, if done, in the abbreviated CTR.

Handling of DMC Analyses

A partially external DMC, independent of the trial and project teams, was set-up on project level to review all available safety data as well as selected efficacy data in an unblinded manner at regular intervals following first-patient-in. A separate DMC SAP which describes the analyses required for assessment by the DMC was produced and finalised prior to first patient randomised into the trial. Further details were provided in a DMC charter.

8. TIMEPOINT OF RELEASE OF TREATMENT INFORMATION

This is an open-label trial with a single arm and the treatment information will be loaded into the trial database.

11. HISTORY TABLE

Table 11: 1 History table

Version	Date (DD-MMM-YY)	Author	Sections changed	Brief description of change
1	20-DEC-21		None	This is the final TSAP
